## **6.10. Subjects**

The study population for this clinical study will be comprised of adult patients who have been diagnosed with acute thrombotic or thromboembolic stroke with onset of symptoms less than 24 hours prior to enrollment. In addition, these patients must satisfy all inclusion and exclusion criteria.

### **6.10.1. Use of OUS Data**

The clinical practice in Europe and Canada for treatment of acute ischemic stroke is very similar to that in the U.S., endovascular device handling and use is identical, and post treatment follow up practices are very similar. These are the non-patient-dependent factors that most affect outcome. The use of IV t-PA is specified per protocol to be used only within three (3) hours of stroke onset for this study. Data generated from different geographies will be evaluated for poolability based on the statistical criteria described in Section 8 and the SAP.

Data collected outside the U.S. will be collected according to GCP as defined in this protocol and other study documents. Human subjects will be protected according to International Conference of Harmonization (ICH) Guidelines for Good Clinical Practice (GCP), ISO 14155:2011, the Declaration of Helsinki, and the pertinent individual country laws/regulations. This study will be conducted in compliance with applicable requirements in the Protection of Human Subjects regulations in 21 CFR part 50, the Institutional Review Boards regulations in 21 CFR part 56, and the Investigational Device Exemptions regulations in 21 CFR part 812.

### **6.10.2. Clinical Practice**

Either CT or MRI are appropriate for screening stroke. Actual endovascular treatment in the US, Canada and Europe occurs in a catheterization laboratory (also known as Cath Lab). Cath lab practices and procedures and follow up care for AIS patients do not differ in a manner that could affect outcome measured with mRS

In both the US, Canada and Europe, patients experiencing an acute ischemic stroke receive lytic IV t-PA (if they are suitable candidates); if this is not effective then they are treated endovascularly with a stent retriever. The investigator may wait 60 minutes to see if the lytics achieve revascularization before mechanical thrombectomy or may initiate revascularization within 60 minutes.

While in the United States, Canada and Europe lytic therapy is recommended for patients meeting the European cooperative acute stroke study (ECASS) inclusion/exclusion criteria between the 0-4.5 hour from stroke onset, IV t-PA is not FDA approved for use after three (3) hours from stroke onset. In this study, IV t-PA usage will be on-label for the US indication and will not be administered after three (3) hours from stroke onset in study Subjects.

There are no other population or location specific treatment differences present between the patient treatment in the U.S. and those in Canada and in Europe which could reasonably be suggested to influence results.

## 7. Assessment of Safety

The following assessment criteria will be used to evaluate the safety endpoint of the study.

### 7.1. Cerebral CT or MR Imaging

This study will collect imaging data in line with routine practice as follows:

- Pre-procedure CT/ MRI
- 24-hour (-8/+12) CT/ MRI

All imaging should be in line with standard of care. No extra imaging should be performed for the purpose of the study. No patient should be exposed to extra radiation as a result of participation. It is preferred that the same imaging modality is used at 24 hour timepoint as at baseline (CT or MRI) to make direct comparison easier. MRI DWI is preferred, CT is acceptable.

Any other imaging performed (for example as a result of clinical deterioration) will also be provided.

In the event of abrupt neurologic deterioration or when deemed necessary by the investigator, an emergency CT or an MR imaging evaluation should be performed. An immediate evaluation of the presence/absence of hemorrhage, edema, and/or infarction as contributors to the clinical deterioration will be made. Any imaging taken prior to the routine 24-hour imaging (which may be taken in a time window of 16-36 hours without becoming a protocol deviation) for this reason will be included in the analysis.

Hemorrhages will be classified clinically and radiologically according to the Heidelberg Bleeding Classification (see definitions section for complete description).

### 7.2. Neurologic Evaluations

Repeat NIHSS determinations are performed in line with standard of care at 24 hours (-8/+12 hrs.) and at seven (7) days (-2/+3 days or discharge whichever is sooner) follow-up time points post-procedure. An additional NIHSS score should be obtained when any signs of neurologic deterioration occur or in the event of an ICH to assess the degree of deterioration. A certified examiner should perform all neurologic evaluations. Follow-up assessments will be conducted by blinded and certified study team member.

## 8. Statistical Analysis

### 8.1. Study Design

The Envi™-SR study is a prospective, multi-center randomized adaptive design where the primary effectiveness endpoint will be assessed via a blinded evaluation of the Modified Rankin Scale (mRS). Up to 30 study centers may participate in this study. A pre-specified interim assessment for conditional power (CP) for potential sample size readjustment will be performed by the independent DMC after 50% of the minimum target ITT sample size (270/2: 135 patients) have been randomized and completed the day 90 evaluation or prematurely discontinued from the study. The purpose of this trial is to provide confirmatory clinical evidence that the Envi™-SR Thrombectomy Device provides benefits similar to those of the Control Devices for LVO strokes.

### 8.2. Sample Size Considerations

The objective of this trial is to demonstrate similar performance after treatment with the Envi™-SR device compared to the expected proportion of good outcomes at 90 days in the Control arm. The expected proportion of good outcomes in the Envi™-SR arm was estimated based on earlier results with Control. A -12.5% non-inferiority margin (NIM) will be used to examine the lower bound of the 1-sided 97.5% exact binomial confidence interval of the difference (Envi™-SR minus Control) in the proportion of patients with a 90-day mRS of 0-2. The null hypothesis and alternative hypothesis are presented below.

Ho: Envi™-SR – Control  $\leq$  -12.5%

Ha: Envi™-SR – Control  $>$  -12.5%

If the lower bound of the 1-sided 97.5% exact binomial confidence interval of the difference (Envi™-SR minus Control) in the proportion of patients with a 90-day mRS of 0-2 is greater than -12.5%, then non-inferiority will be established.

The planning estimates for the Envi™-SR study considered the lower bound of the 2-sided 95% (asymptotic) confidence interval from the SWIFT PRIME study for estimation (50.5%). Sample size estimates were prepared for this parallel design study assuming a non-inferiority margin of -12.5% (Envi™-SR successes [%] minus Control successes [%]). Under the alternative hypothesis, non-inferiority would be claimed if the lower bound of the 1-sided 97.5% confidence interval of the difference is less than the non-inferiority margin of -12.5%. All planning estimates are performed for the ITT population as this is the primary population for analysis.

For planning purposes, the estimated effectiveness of the Control device was based on a previously published meta-analysis of 5 randomized trials in which the effectiveness of endovascular thrombectomy over standard medical care was shown. This study was referred to as the HERMES collaboration. Of the 633 included participants that received thrombectomy, 46.0% (291) achieved a good outcome based on an mRS score  $\leq$  2 at 90 days. The expected effectiveness of the Envi™-SR thrombectomy device was based on the SWIFT PRIME study where 98 patients were treated with the Control FR (Flow Restoration) or Control 2 device. In total, 59 out of the total 98 patients who were treated achieved an mRS score less than or equal to 2. As the reported 60% patients with good outcome in the SWIFT PRIME study might be an overestimation of the actual result, the lower bound of the 95% CI was calculated based on a normal approximation. The construction of a confidence interval around the estimate of SWIFT PRIME yielded a 95% CI of [50.5% - 69.9%].

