---------------------------	--

	30.The patient is in a coma.
--	------------------------------

Statistics	
This prospective, multi-center randomized adaptive clinical study is composed of three (3) phases: screening, procedure, and follow-up. The analyses to address the primary and secondary objectives will be based on the data collected during the procedure and follow-up period. There is a single primary effectiveness endpoint and a primary safety endpoint. There are five (5) secondary endpoints that will be evaluated statistically in hierarchical order. The results from the fourteen tertiary endpoints will be summarized and compared between the two (2) randomized treatment arms as supportive information.
 
The non-inferiority margins for the primary and secondary endpoints come from five (5) published reference studies using retrieval devices in a similar subject population. Where a non-inferiority margin is not available from the peer-reviewed literature, the confidence limit of the difference (Envi™-SR minus Control) in the proportion of subjects experiencing the event of interest, establishing non-inferiority will require zero to be contained within the 1-sided 97.5% or 2-sided 95% confidence limits.
 
The target Intention to Treat (ITT) sample size for this clinical investigation is 270 subjects: 135 subjects per arm. An interim assessment based on conditional power (CP) will be performed by the independent Data Monitoring Committee (DMC) after 50% of the target ITT enrollment (135 subjects) has been randomized and either completed the 90-day (<math>\pm 15</math> days) evaluation visit or withdrawn prematurely. The interim assessment may result in the target enrollment being increased to a maximum of 560 subjects consented and enrolled. Following the interim assessment, the DMC will provide a non-binding recommendation to the sponsor to either continue enrolling to the target sample size, increase enrollment up to the maximum sample size, or stop the study for futility (<math>CP < 37\%</math>).
 
At the time of the interim assessment performed by the DMC, the Committee will receive data on all adverse events, effectiveness, investigational site, time last seen well (TLSW), and Additional Therapy for each patient. Through inspection of the tabulated data the DMC will be tasked with examining if data are consistent with planning estimates as described in the DMC Charter.
 
The Intention to Treat (ITT) population will include all subjects that have signed the informed consent form (ICF) and were randomized. The primary population for the primary and secondary analyses for this study will be the ITT population. The ITT population will also serve as the Safety population.
 
Randomization to either Envi™-SR or Control will be performed in a 1:1 ratio, stratified by six (6) factors using a dynamic randomization scheme:
 
 
• Age: <math>\geq 67</math> and <math>< 67</math>
 
• Site of occlusion: ICA, MCA M1, MCA M2
 
• Baseline/Enrollment NIHSS score: <math>< 17</math> and <math>\geq 17</math>
 
• Prior IV t-PA usage: Yes and No
 
• Time to symptom onset: <math>\geq 6</math> hours and <math>< 6</math> hours
 
• Baseline ASPECTS: 6-7 and 8-10
 
 
This randomized study will ensure that the assessing clinical team are blinded to treatment assignment. Due to the nature of the treatment, and access to the patient records, the treatment team is not required to be blinded. The treatment team will obtain a randomization assignment using a web-based randomization system.
 
The primary effectiveness and safety endpoints will be evaluated simultaneously. If the primary effectiveness endpoint is met (Envi™-SR non-inferior to Control), the secondary effectiveness endpoints will be evaluated statistically in the hierarchical order presented in this protocol and the Statistical Analysis Plan (SAP).

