### Maximum Sample Size

If the gap narrows between the 2 randomized groups to 49.5% (Control) and 50.5% (Envi™-SR), 426 total patients (ITT) will be required (type 1 error rate of 2.5%, power of 80%). A loss to follow-up rate of 5% or less is expected. Missing data will be imputed as described in section 8.2.2. As multiple imputation could dampen the signal from the subject data that is imputed, an additional 5% of subjects may be added to compensate for any potential impact, leading to a total sample size of 448 subjects (ITT).

All estimates are performed based on the ITT population. However, all enrolled subjects (i.e., consented), including enrolled screen failures, will count toward the maximum sample size of 560 patients. The rate of enrolled screen failures is not expected to exceed 25%. Therefore, the maximum sample size for enrollment will be the ITT maximum sample size plus 25%, or 560 patients.

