### 8.2.2. Missing and Censored Data

Missing data, which in this instance is defined as data that was not entered into the EDC system for analysis, may have an impact upon the interpretation of the trial data.

The primary presentation of the results for the primary and secondary endpoints using the ITT population will be based on the observed data with multiple imputation for missing endpoint data using SAS PROC MI. This procedure uses an iterative modeling approach to generate estimates for patients who withdraw prematurely, or the data is just not recorded, incorporating

multivariate imputation by fully conditional specification (FCS) methods. The discriminant function method will be used for classification variables. With the function method of classification, the missing values will be imputed sequentially in the following order:

- Age: ( $\geq 67$  and  $< 67$ )
- Site of occlusion: ICA, MCA M1, MCA M2
- Baseline/Enrollment NIHSS score ( $< 17$  and  $\geq 17$ )
- Prior IV t-PA usage (Yes / No)
- Time to symptom onset ( $\geq 6$  hours and  $< 6$  hours)
- Baseline ASPECTS (6-7 and 8-10)

Each missing score will be imputed ten times to generate ten imputed complete datasets based on the Markov Chain Monte Carlo (MCMC) method with age, occlusion site, NIHSS score ( $< 17$  /  $\geq 17$ ), baseline ASPECTS (6-7 / 8-10), prior IV t-PA usage (yes / no), and time to symptom onset ( $\geq 4$  hours /  $< 4$  hours) entered into the model following this sequential order. The imputed score will be rounded to the first decimal point for continuous variables. Proc MIANALYZE will be used to combine the imputed datasets to render an analysis of the binary outcomes for the results for the primary effectiveness and safety endpoints and the applicable 4 secondary endpoints. The relevant secondary endpoint analysis will follow the method outlined to calculate the odds ratio with the imputed dataset.

Additional sensitivity analyses will also be conducted as a secondary examination of the primary analysis using the last observation recorded following the procedure observation carried forward. A tipping point analysis will also be conducted.

If a patient did not have solicited adverse events of special interest [incidence by type of event] prior to withdrawing prematurely from the study, the patient will be considered as not having experienced the event.

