## 8.3. Analysis Methods

### 8.3.1. Primary Effectiveness Endpoint

The primary effectiveness endpoint of this study maps to the primary efficacy objective and addresses the following research question:

*At 90 days ( $\pm 15$  days) following the study index procedure, is the lower bound of the 1-sided 95% confidence interval of the difference (Envi™-SR minus Control) in global disability ( $mRS \leq 2$ ) above the a priori threshold of -12.5%? This is a 1-sided evaluation to establish non-inferiority.*

The hypothesis is that the proportion of good outcomes ( $mRS \leq 2$ ) at 90 days after treatment with the Envi™-SR thrombectomy device in patients with cerebral infarction is non-inferior to the rate of good outcome at 90 days after treatment with the Control device. The largest clinically acceptable effect to be able to declare non-inferiority is -12.5% (non-inferiority margin). The null and alternative hypotheses can be defined mathematically as follows:

- Ho: Treatment with Envi™-SR is inferior to treatment with Control for good outcomes defined as an  $mRS \leq 2$  at 90 days based on a non-inferiority margin of -12.5% (good outcome with Envi™-SR  $<$  [good outcome with Control – 12.5%]).

- Ha: Treatment with Envi™-SR is non-inferior to treatment with Control for good outcome defined as an mRS  $\leq 2$  at 90 days based on a non-inferiority margin of -12.5% (good outcome with Envi™-SR  $\geq$  [good outcome with Control – 12.5%])

The SAS code to generate these summary statistics and addressing missing mRS data at 90 days post-procedure is presented in the Statistical Analysis Plan. If the lower bound of the 1-sided 97.5% confidence interval of the difference (Envi™-SR minus Control) in global disability is numerically greater than -12.5%, Envi™-SR will be considered non-inferior to Control.

Additional therapies are defined in Section 3.5. The primary effectiveness endpoint will be derived 3 ways:

Method 1: mRS based on the observed results, independent of the use of additional therapies to retrieve the clot. Multiple imputation will be used to impute the mRS score for patients who become lost to follow-up prior to the 90 day evaluation.

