Method 2: mRS based on the observed results for patients where additional therapies were not used to retrieve the clot. Subjects who required additional therapy for reperfusion failure or additional off-label therapies to retrieve the clot will be automatically treated as primary effectiveness endpoint failures. Multiple imputation will be used to impute the mRS score for patients who become lost to follow-up prior to the 90 day evaluation.

Method 3: mRS based on the observed results for patients where additional therapies were not used to retrieve the clot. Subjects who required any additional therapy to retrieve the clot will be automatically treated as primary effectiveness endpoint failures. Multiple imputation will be used to impute the mRS score for patients who become lost to follow-up prior to the 90 day evaluation.

An important consideration in requiring any patient who received additional therapy to retrieve the clot is acknowledging this is truly a random effect. The observed mRS at 90 days could indicate no difference in functional independence between the 2 randomized treatment groups, but the use of additional therapies could, by chance and chance alone, result in non-inferiority being achieved or lost. For this reason, Method 1 is the primary method for the derivation of the primary effectiveness endpoint for the study; Method 2 and Method 3 represent secondary derivations of the primary effectiveness endpoint.

Two (2) additional sensitivity analyses will be prepared to explore alternative methods for imputation for patients who are lost to follow-up (ref. Section 5.4) for the primary endpoint. The first sensitivity analysis will impute the baseline value for the 90-day result, functionally resulting in no change from baseline. The second sensitivity analysis will be conducted imputing the worst score at 90-days recorded for a patient within their respective treatment group for patients who are lost to follow-up. Additional details are provided in the SAP.

Additionally, as a final sensitivity analysis of the primary endpoint, a logistic model will be performed within the imputed datasets derived using multiple imputation. This model will incorporate the stratification variables specified in the randomization as covariates and with randomization group assignment. Under the guise of a sensitivity analysis, separate sub-group analysis will be prepared to examine factors that may have influenced the 90-day mRS scores.

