#### **8.3.4. Evaluating the Effect of Different Clinical Sites and Regions (US vs. OUS) and the Effect of Clinical Sites with Low Patient Enrollment**

The method to be applied for examining the effect of different clinical sites will facilitate the generation of adjusted estimates to contrast against the unadjusted estimates. The adjusted estimates for the primary effectiveness and safety endpoints will introduce the effect of different clinical sites; the unadjusted estimates for the primary effectiveness and safety endpoints will only consider the randomized treatment assignment in the model. This sensitivity analysis will address the fundamental question relative to the effect of clinical sites and is considered more informative than simply adding an interaction term into the model for analysis. To provide further insight into the results, the model will be run with the interaction term retained for treatment and clinical site.

To assess the effect of small clinical sites, sites with lower enrollment will be defined as having  $\leq 2$ , 3, 4, 5, and 6 patients. For each dataset with small sites defined as having  $\leq 2$ , 3, 4, 5, and 6 patients, a random effects model will be used to calculate the overall estimate adjusted by clinical site. The general framework of the random effects model will adjust for variability both among the clinical sites and variability within the clinical sites. The model that will be used to derive the estimates and the standard errors is presented in the SAP. This model will be used to assess the primary effectiveness and safety endpoints. From the solution for fixed effects, the exponentiation of the estimates and the standard errors will provide adjusted confidence limits to assess the effect adjusted for clinical sites.

To assess the effect of geographic location, a random effect model will be used to calculate the overall estimate adjusted by the location of the investigational site (US vs. OUS). The model that will be used to derive the estimates and the standard errors is presented in the SAP. This model will be used to assess the primary effectiveness and safety endpoints. From the solution for fixed effects, the exponentiation of the estimates and the standard error will provide adjusted confidence limits to assess the effect adjusted for geographic location.

The testing strategy and exact model for analysis will be included in the Statistical Analysis Plan (SAP).

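### The primary decision rule names an exact binomial limit that does not fit the planned pooling of imputed datasets, and it leaves out the six randomisation factors

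*Combined protocol and SAP*

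**What the plan says.** **Decision rule.** Section 8.2 opens its success criterion with: "If the lower bound of the 1-sided 97.5% exact binomial confidence interval of the difference (Envi™-SR minus Control) in the proportion of patients". That bound must lie above −12.5%. The same section names the exact interval once before, when it sets out the margin. The synopsis and section 8.3.1 give the same one-sided 97.5% rule without naming an interval method. No covariates enter.

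**Missing data.** Method 1, the primary derivation in section 8.3.1, imputes missing 90-day mRS. Section 8.2.2 generates ten completed datasets and adds: "Proc MIANALYZE will be used to combine the imputed datasets to render an analysis of the binary outcomes". The SAS code is deferred to the SAP, and no SAP code is in the document available.

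**Randomisation factors.** Under Statistics, the synopsis says that allocation is "stratified by six (6) factors using a dynamic randomization scheme": age, occlusion site, NIHSS, prior IV t-PA, onset time and ASPECTS. They return in the imputation model (8.2.2) and in a logistic model that 8.3.1 places last among the sensitivity analyses: "This model will incorporate the stratification variables specified in the randomization as covariates".

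**Other adjusted models.** For site and region, section 8.3.4 says that "the exponentiation of the estimates and the standard errors will provide adjusted confidence limits". Sections 8.3.5 to 8.3.7 use nearly the same words for control device, device size and time last seen well.

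**The concern.** Three things are at stake.

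1. The interval that decides the trial is not settled. One section calls for exact limits and another for a pooling step that cannot take them. Someone must choose later, possibly after data have been seen.
2. When allocation is balanced on factors that predict outcome, a crude standard error still counts the variation that balancing removed. The interval is then wider than it need be, and precision already bought by the randomisation scheme is given up.
3. The margin is a difference of 12.5 percentage points. A logistic or exponentiated random-effects estimate is an odds ratio, and the protocol sets no odds-ratio margin. As described, these adjusted models give nothing to compare with −12.5 points. Read literally, exponentiating a standard error does not give a confidence limit either.

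**Working it through.** **Inputs.** Margin m = 0.125; one-sided α = 2.5%; 1:1 allocation; rates 46% and 50.5% for the target size, 49.5% and 50.5% for the maximum; loss to follow-up of 5% or less; ten imputations (sections 8.2, 8.2.2, 6.8.2.7). Power of 80% is printed only beside 426, and is taken to apply to 270 as well.

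**1. Reproduce the plan's sizes.** The Farrington-Manning score formula, per arm, is

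n = [(z₀.₉₇₅√V₀ + z₀.₈₀√V₁) / (m + p_T − p_C)]²

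V₁ is the sum of p(1−p) at the planning rates. V₀ is the same sum at the rates fitted under a true difference of −12.5 points.

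- Target: null rates 54.57% and 42.07%, V₀ = 0.4916, V₁ = 0.4984. n = [(1.960×0.7012 + 0.8416×0.7060)/0.17]² = 134.07, so 135 per arm, **270**.
- Maximum: null rates 56.25% and 43.75%, V₀ = 0.4922, V₁ = 0.49995. n = [(1.960×0.7016 + 0.8416×0.7071)/0.135]² = 212.97, so 213 per arm, **426**.

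The same formula gives the 318 stated for the safety endpoint. The simpler unpooled formula gives 272 and 432. The planning therefore assumed an asymptotic, unadjusted test.

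**2. What an exact test would cost.** Power by full enumeration of the two binomials:

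| N | Rates | Score | Exact unconditional |
|---|---|---|---|
| 270 | 46 / 50.5% | 79.3% | 78.9% |
| 426 | 49.5 / 50.5% | 79.9% | 79.9% |
| 448 | 49.5 / 50.5% | 82.1% | 79.6 to 81.4%, by ordering |

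The cost is 0 to about 2.6 points (82.13 − 79.56 at most). Exactness is an inconsistency more than a power problem.

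**3. Pooling.** With M = 10 estimates Q_j and squared standard errors U_j, Rubin's rules give T = Ū + (1 + 1/M)B, where B is the variance of the Q_j, and a lower limit Q̄ − 1.96√T. Every term U_j is needed. An exact limit comes from inverting a test and supplies none. A risk difference with a Wald standard error does supply it. In 20,000 simulated trials with 5% missing at random and imputation without covariates, pooled power was 77.6% at 270 and 79.4% at 448, against 78.9% and 82.2% with complete data. Type I error was 2.5% and 2.4%.

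**4. Leaving out the six factors.** Let R² be the share of outcome variance that they explain. The documents give no value, so it is assumed. At N = 270 and planning rates,

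SE = √[0.498375(1 − R²)/135], power = Φ(0.17/SE − 1.96).

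At R² = 0, SE = 0.0608 and power = Φ(2.798 − 1.960) = 79.9%.

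| R² (assumed) | 0 | 0.05 | 0.10 | 0.25 |
|---|---|---|---|---|
| Power at 270 | 79.9% | 81.9% | 83.9% | 89.8% |
| N for 80% power | 272 | 258 | 244 | 204 |

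For the crude test, if balance on the factors were complete, the true type I error would be about Φ(−1.96/√(1−R²)): Φ(−2.066) = 1.9% at R² = 0.10 and Φ(−2.263) = 1.2% at 0.25, against a nominal 2.5%.

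**5. Scale of the other analyses.** Methods 2 and 3, the baseline-value and worst-score imputations, last observation carried forward and the tipping-point analysis all keep the binary endpoint, so each can yield a risk difference. The stratification-factor logistic model and the models in 8.3.4 to 8.3.7 do not, as described. For an odds ratio, limits are exp(estimate ± z×SE).

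**The case against.** The exact interval is named only in section 8.2, which deals with sample size. The synopsis and section 8.3.1 do not specify it, and the code is left to the SAP. A reader might infer that the primary analysis cannot be run. The documents do not support that: a risk difference with a standard error pools without difficulty, and the SAP code may already do this. What remains is that 8.2 states the success criterion itself, so it needs correcting even if the code is sound.

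An unadjusted primary test with an adjusted sensitivity analysis is a legitimate and conservative choice. The sample size was computed for it, and no inflation of type I error follows. This stands. Adjustment is an improvement in efficiency, and its gain is zero if the factors do not predict outcome. Nor are the factors ignored altogether, since they enter the imputation and one sensitivity model.

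Sections 8.3.4 to 8.3.7 aim to contrast adjusted with unadjusted estimates, not to repeat the margin test, and the phrase about exponentiating may be shorthand. Both readings are fair. A contrast on the odds-ratio scale still does not show whether adjustment would move the conclusion across −12.5 points.

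**Conclusion.** The point holds in limited form. The exact limit in 8.2 conflicts with the pooling in 8.2.2 and with the score formula behind 270 and 426. The primary test omits the six randomisation factors, which makes it conservative if they are prognostic. One group of sensitivity models is not on the margin's scale.

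The size is uncertain. Exactness costs at most about 2.6 power points. Omitting the factors costs nothing at R² = 0 and about 2, 4 and 10 points at 0.05, 0.10 and 0.25, taking variance to shrink by 1 − R². No adjusted estimator was simulated, so control of type I error under adjustment rests on large-sample theory.

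Three stronger inferences are not supported:

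- That the sample size is wrong. It is correct for an unadjusted test.
- That no robustness analysis can test the non-inferiority conclusion. Those listed first in step 5 can.
- That power at equal rates with 270 subjects describes the trial. The interim assessment may raise the ITT size to 448.

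**What to change.** 1. In section 8.2, delete the reference to an exact binomial interval.
2. In 8.2, 8.3.1 and the SAP, name one primary estimator: the marginal risk difference standardised from a logistic model with arm and the six randomisation factors, with a robust or delta-method standard error in each imputed dataset, pooled by Rubin's rules. Compare its lower one-sided 97.5% limit with −12.5%.
3. Pre-specify a fallback if the model does not converge, and keep the unadjusted pooled risk difference as a sensitivity analysis.
4. Report the models in 8.3.1 and 8.3.4 to 8.3.7 as risk differences. Where odds ratios are kept, state that limits come from exponentiating estimate ± z×SE.
5. While editing, reconcile three neighbouring statements: the one-sided 95% level in the 8.3.1 research question against 97.5% elsewhere; the sentence in 8.2 that claims non-inferiority when the bound is less than the margin; and the onset-time cut in the imputation model, given as both 6 and 4 hours in 8.2.2.

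The cost is slightly more complex SAP wording and code. Margin, α, sample size and data collection do not change. If the sponsor prefers an unadjusted primary test, steps 1, 4 and 5 and a named pooled risk difference still resolve the inconsistency. The change should be final before the interim assessment at 135 subjects.
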